After enrollment and prior to the first assessment, participants will be assigned to the intervention or the control group through randomization by minimization. MinimPy will be used to randomize the participants based on age (2 levels: <8 years and >8 years) and GMFCS score (3 levels: I, II and III) (Saghaei, 2011). The allocation ratio will be 1:1 with probability set at 0.75. The biased coin minimization will be used as probability method and marginal balance as distance measure.

Assessments are planned in the University Hospitals and special needs schools, at baseline (PRE) and after the 12-week control or intervention period (POST). Training and assessments will always be

conducted on different days. Participants in the intervention group start training within 2 weeks after the baseline assessment. For both groups, the POST assessments will be performed within 1 week after the 12-week period. Blinding is not completely possible since participants and trainers are aware of group allocation. Assessors are also aware of group allocation during assessments but data will be anonymized before processing and analyses. The participants will be assessed by the same assessors (PRE and POST) and the data of one participant will be processed by the same processor.

Piloting for the feasibility of the measurements and parameter extraction was done through prior and parallel investigations. The exercises used during the training were piloted through iterations with strength and conditioning specialists to ensure correct exercise selection and also with senior pediatric physiotherapists and their patients to ensure the applicability in targeted population of children with SCP.

Sample size

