Participants assigned to the control group will continue their usual care. Participants assigned to the intervention group will undertake 3 to 4 PRT sessions per week (alternating), on non-consecutive days, for 12 weeks, resulting in a total of 42 scheduled sessions. The PRT program will be explained during a visit to the physiotherapist(s) and parent(s). After a familiarization phase of up to 3 sessions, the official PRT starts. At least 1 session per week will be performed under the supervision of the physiotherapist(s). The remaining sessions will be completed at home under the supervision of a parent or guardian. We will create a patient-specific PRT program through the online software platform Skill-Up (www.Skill-up.com) and ask the participants to log each PRT session in a training diary. Throughout the 12-week period, the PRT program will be supervised through phone calls, e-mails, and targeted visits to check adherence and progress exercises by trainers with a background in human movement sciences. Participants in the intervention group were invited for an interim

assessment after 6 weeks, which was also used as an additional moment to evaluate and adjust the intensity of the training program.

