Age, body mass and height will be recorded for the participants at each assessment. Usual care and treatment history will be recorded at the PRE-assessment using standardized in-house questionnaires. A routine clinical examination regarding the investigated muscle groups will be performed, including passive joint range of motion, spasticity, manual muscle strength and selective motor control (SMC), based on standard clinical scales (Bohannon & Smith, 1987; Boyd, 1999; Gage et al., 2009; Matthews, 1977). These clinical examination parameters will be used to define the most affected leg for bilaterally affected children. If both sides are equally affected, the right leg will be used. Lower limb SMC will be assessed with the selective control assessment of the lower extremity total limb score (Fowler et al., 2009). Assessments will be performed in the same order, starting with clinical examination and muscle morphology, followed by isometric and functional strength and lastly gross motor function and walking capacity.

2. Isometric strength assessments

Knee extensor, knee flexor and plantar flexion maximum voluntary isometric contractions were collected with a fixed dynamometer in a previously described, custom-designed chair (Goudriaan et al., 2018). The dynamometer is positioned at 75% of the lower leg and foot length, and the level arm distance is measured between this position and the joint axis. After a test trial, we aim to collect 3 well executed maximum voluntary isometric contractions with a duration of 3 to 5 seconds. Standardized verbal encouragement and visual feedback will be provided throughout the isometric contraction. The protocol includes periods of rests of at least 10 seconds between repeated

assessments and of at least 2 minutes between different muscle groups. Peak force is extracted from each trial with a custom-written MATLAB script and maximal joint torque (in Nm) will be calculated by multiplying peak force with the lever arm and taking the average of the 3 trials. Knee and plantar flexion maximal voluntary isometric contractions are corrected for gravity by subtracting the gravitational torque in rest from the outcomes. Maximal joint torque will be normalized by dividing it by body weight (Nm/kg).

3. Three-dimensional freehand ultrasonography

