Endurance functional strength will be assessed with 30-s repetition maximum tests including bi- and unilateral heel raise, sit-to-stand, and lateral step-up, as previously described (van Tittelboom et al., 2021). Participants completed as many repetitions as possible in 30 seconds. Each test will be 3 times and the average taken as final score. Explosive strength will be evaluated with a standing long jump, with both feet together, which will also be repeated 3 times and the scores averaged. The use of orthoses will not be allowed, as the PRT program will also be performed without orthoses.

5. Gross motor function and walking capacity

Gross motor function will be evaluated with the Gross Motor Function Measure-Item Set (Brunton & Bartlett, 2011) and the Gross Motor Ability Estimator 2 used to estimate the final score. The 1-minute walk test, performed on an indoor 20-m track, will be used to assess walking capacity (Chrysagis et al., 2014; McDowell et al., 2009). The participant will be instructed to walk as fast as possible without running and the distance covered in 1 minute will be recorded. Both assessments will be performed without orthoses, but a key-walker is allowed for the 1-minute walk test for children classified as GMFCS-level III.

6. Statistics

Descriptive statistics for all groups will be summarized using appropriate summary indices. The comparison between TD children and children with CP will be performed with a Student's *t*-test (after confirming equality of variances) or the Mann-Whitney *U*-test. Associations between muscle morphology measures, muscle strength and participant characteristics will be evaluated with univariate linear regressions followed by a multivariate linear regression using a backward approach. The linear regressions in the TD cohort based on an anthropometric variable will be used to define the deficits in muscle strength and muscle morphology in CP children.

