To define the effects of the PRT intervention linear mixed models will be applied to evaluate the difference in evolution over time between the control and intervention group (time*group interaction effect) and between PRE and POST within each group (time effect). The random effects in these models can correct for the correlation between repeated observations within the same subject. Moreover, in the case of missing values that are completely at random, i.e. not related to any observed or unobserved outcomes, or at random, i.e. related to observed outcomes, linear mixed models provide valid inferences for missing observations. A covariance structure for repeated measurements to model longitudinal dependencies within the participant will be applied with a random intercept for participant (legs are nested within participants). The models will be adjusted for age and GMFCS level as covariates as these were used to allocate the children to the control or intervention group. Age was entered as a categorical variable (<8 years and >8 years). A full-factorial time*group mean model adjusted for age and GMFCS level, with a compound symmetry covariance matrix, unless an unstructured covariance matrix results in a better fit (Akaike information criterion decrease of >2). Adjustment for age (categorical variable: <8 years and >8 years) and GMFCS level will be included as these were used to allocate the children to the control or intervention group.

The α -level will be adjusted to $p \leq 0.01$ since multiple parameters are evaluated for most research questions, with a maximum of 5 parameters (functional strength). All analyses will be performed with SPSS (Version 28, SPSS Inc., Chicago, Illinois).

Finally, the data of the total intervention group (intervention + waitlist control group with delayed intervention) will be used to define the association between baseline properties and the changes in the outcome parameters after PRT with uni- or multivariate regression (mixed) models.

References

<https://doi.org/10.1016/j.jclinepi.2003.12.013>

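### Only the intervention group is invited to a 6-week interim assessment; if outcome tests are run there, any practice gain on effort-dependent outcomes may be counted as a training effect

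*Combined protocol and SAP*

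**What the plan says.** The Study design section plans assessments for both groups "at baseline (PRE) and after the 12-week control or intervention period (POST"), and names no other time point.

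The Intervention section adds a further visit for one arm only: "Participants in the intervention group were invited for an interim". The same sentence then gives its timing and a second purpose: "assessment after 6 weeks, which was also used as an additional moment to evaluate and adjust the intensity of the training program". For the other arm it says: "Participants assigned to the control group will continue their usual care". No control visit at week 6 appears anywhere in the document.

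The Statistics section uses linear mixed models to "evaluate the difference in evolution over time between the control and intervention group (time*group interaction effect"), together with PRE-to-POST change within each group. On adjustment it says: "The models will be adjusted for age and GMFCS level as covariates". There is no term for the number of test sessions and no stated role for week-6 data.

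**The concern.** Several outcomes depend on maximal effort and on knowing the test. For isometric strength the plan says: "After a test trial, we aim to collect 3 well executed maximum voluntary isometric contractions". For the 30-second tests: "Participants completed as many repetitions as possible in 30 seconds". The long jump, the gross motor items and the fast 1-minute walk are of the same kind. The participants are children aged 5 to 11 at baseline, so some gain from having done a test before is plausible.

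If these tests were run at week 6, an attending intervention child arrives at POST having been tested twice, and a control child once. Any gain from the additional session would enter the time*group interaction, which is the estimate of the training effect. Adding the number of sessions as a covariate would not solve this, because that number is nearly the same variable as group.

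**Working it through.** **1. What the text establishes about week 6**

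| Question | What the document gives |
|---|---|
| Who is invited | Intervention group only (Intervention) |
| Purpose | Called an assessment and *also* used to adjust training, so adjustment was not its only use |
| Tests performed | Not listed; the outcome-measure sections do not mention the visit |
| Attendance | By invitation; no number given |
| Role in the analysis | None stated; the contrasts described are PRE and POST (Statistics) |

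The wording points towards outcome testing. So does the fact that training review is already provided for by targeted visits and by difficulty checks at least every two weeks. This is an inference, not a statement in the plan.

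**2. Reproducing the plan's sample size**

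Inputs from the Sample size section: d = 0.8, alpha = 0.01, power 80%, independent samples t-test. Sidedness is not stated. Power comes from the non-central t distribution with 2n − 2 degrees of freedom and non-centrality d × √(n/2).

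- n = 38, two-sided: power 0.798.
- n = 39, two-sided: non-centrality 0.8 × √19.5 = 3.53, critical value 2.642, power 0.810.

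So 39 is the smallest n that reaches 80%, as stated. Design effect: 39 × 1.1 = 42.9, rounded to 43 legs; 43 / 2 = 21.5, rounded to 22 bilaterally affected participants. Both figures reproduce.

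**3. What a practice gain would do to the test**

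The document gives no practice gain. *Assume* that the extra session adds b SD of the change score in the intervention arm, that every child attends, and that training has no true effect. The chance of p ≤ 0.01 in either direction is then the power formula with b in place of d. For example, at n = 39 and b = 0.2 the non-centrality is 0.2 × √19.5 = 0.883 and the rejection probability is 4.4%.

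| Assumed gain b | Share of d = 0.8 | 39 per group | 22 per group (one value per child) |
|---|---|---|---|
| 0 | 0% | 1.0% | 1.0% |
| 0.1 | 12.5% | 1.7% | 1.4% |
| 0.2 | 25% | 4.4% | 2.7% |
| 0.3 | 37.5% | 10.0% | 5.3% |

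**4. Partial attendance**

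*Assume* that half attend. The mean shift is then b / 2, ignoring the small change in spread from mixing attenders and non-attenders.

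| Gain in attenders | Mean shift | 39 per group | 22 per group |
|---|---|---|---|
| 0.1 | 0.05 | 1.2% | 1.1% |
| 0.2 | 0.10 | 1.7% | 1.4% |
| 0.3 | 0.15 | 2.8% | 1.9% |

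**The case against.** The strongest reply is that the key premise is not in the document. The plan never says which tests were done at week 6, and attendance was by invitation. This stands, and it makes the point conditional.

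Second, training itself supplies much of the familiarity. By week 6 about half of the 42 scheduled sessions, roughly 21, have taken place. They include functional multi-joint exercises and, at least every two weeks, a maximal last set. What one test session some six weeks before POST adds to this may be small. This also stands. It bears on the size of the gain and leaves the difference in test exposure in place.

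Third, the test trial before the isometric contractions and the averaging of three trials for isometric and functional strength limit gains from inexperience. They apply in both arms, however, and do not equalise the number of sessions.

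Fourth, assessors know the allocation. That is a separate issue, present at PRE and POST whether or not there is a week-6 visit, and it adds nothing here.

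A reader might infer that a practice gain has been shown to be counted as a training effect on every effort-dependent outcome, always in favour of training. The document does not support this: it gives neither the week-6 tests, nor the attendance, nor any practice gain. A gain from practice would be expected to favour the intervention group, but its existence and size are not shown.

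**Conclusion.** The asymmetry is in the text, nothing in the control arm mirrors it, and the planned model cannot separate it from training. Whether it biases the result depends on two unstated facts, the tests run at week 6 and the number who attended, and on a practice gain that the document does not give. With no gain there is no bias. At the low end of the assumed range the effect on the error rate is slight; the 10.0% figure needs a gain of 0.3 SD, full attendance and 39 independent observations per group.

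The point is limited to performance outcomes. Muscle volume, muscle length and echo-intensity from ultrasound do not depend on the child's test performance and should be nearly unaffected. Within those limits the plan should be changed, because the exposure is easily avoided.

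**What to change.** Keep the week-6 visit for reviewing the training programme, but do not run the effort-dependent outcome tests there; ultrasound may stay. Both groups then reach POST after one prior test session. The cost is the loss of mid-course performance data, which have no control comparison and no planned analysis. Test time is saved.

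The past tense in the Intervention section suggests that some visits may already have taken place. For children already tested:

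- report which tests were done at week 6 and how many children attended;
- state the limitation for performance outcomes;
- treat the ultrasound outcomes as less open to this bias.

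Do not rely on comparing intervention children who attended with those who did not. Attendance was not randomised, attenders may differ in motivation or adherence, and each subgroup is smaller than one arm. Leaving week-6 data out of the model is no remedy either: the Statistics section already describes PRE and POST only, and any practice gain would still be present in the POST values.

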The PRT program, targeting strength and hypertrophy of knee extensors, knee flexors and plantar flexors, will be prescribed in close consultation with the personal physiotherapist(s) to ensure feasibility for each participant. The general session design recommendations include a 5-minute dynamic warm-up and a 5-minute cool-down. Depending on the participants' abilities, the PRT will start with 1-3 functional multi-joint exercises, followed by 2-3 single-joint exercises targeting the specific muscle groups, all performed without orthotics. Following international guidelines for youth resistance training of the National Strength and Conditioning Association, as well as CP-specific recommendations, the initial exercises start at a training volume of 3 sets of 10 repetitions, aiming at an exercise intensity of 60 to 80% of the estimated 1-repetition maximum, with a rest period in between sets of at least 1 minute (Faigenbaum et al., 2009; Lloyd et al., 2014; Noorduyn et al., 2011; Verschuren et al., 2016). The most difficult exercise that could be performed, with the maximal load that could be lifted, for the defined number of repetitions and sets was defined through trial and error (Moreau, 2020). Throughout the training program, exercise difficulty was increased. Thereto, physiotherapists will be encouraged to regularly test the difficulty of the exercises, i.e. at least biweekly, by asking a maximum performance in the last set, based on exercise execution and fatigue. The intensity will be modified by the trainers or the physiotherapist(s) if the last set exceeded 15 well-executed repetitions. Exercise modification options are dependent on the exercise and include addition of weight in a weighted vest (0.5kg increments up to 10kg), use of a stronger resistance band (5 colors ranging from light to very heavy), increase of ankle weight (1.0, 1.5 or 2.0kg), or selection of a more challenging exercise. The number of sets and repetitions performed, modifications or compensations, perceived fatigue at the end of the session and potential adverse events will be noted in the training diary.

Assessments and outcome measures

1. Participant characteristics

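### Adverse events are collected only through the training-session diary, so the randomized 12 weeks provide no usual-care rate to compare them with

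*Combined protocol and SAP*

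**What the plan says.** The Intervention section lists what goes into the diary: sets and repetitions, modifications or compensations, and fatigue after the session. It adds that "potential adverse events will be noted in the training diary". The same section explains what the diary is. The team will "ask the participants to log each PRT session in a training diary", so an entry belongs to a training session.

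For the other arm the section says only this: "Participants assigned to the control group will continue their usual care". After the control period these children were offered the training (Study outline).

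The contacts during the 12 weeks belong to the training: "the PRT program will be supervised through phone calls, e-mails, and targeted visits to check adherence and progress exercises". The 6-week visit is also limited to one arm: "Participants in the intervention group were invited for an interim" assessment. Under Study design, both groups are assessed at PRE and at POST. Under Participant characteristics, "Usual care and treatment history will be recorded at the PRE-assessment using standardized in-house questionnaires", and no later record of care or events is described.

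**The concern.** Children with spastic cerebral palsy can have pain, falls and minor injuries whether or not they train. A count from the trained arm alone cannot separate events due to training from events that would have happened anyway. The trial randomizes against usual care, so it could supply that background rate, but the plan describes no way of recording it.

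There is a second, smaller gap inside the trained arm. If events are written down per session, a child who misses or stops sessions has no session entry in which to record one.

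What is at stake is the description of tolerability. Families and physiotherapists will want to know how the program was tolerated, given that it uses added load and that most sessions take place under a parent's supervision. The strength, morphology and function results are not at stake.

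**Working it through.** The point is structural, so the main check sets the relevant parts of the document side by side and looks for any other route by which an event could be recorded.

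| Possible route | Trained arm | Control arm, first 12 weeks |
|---|---|---|
| Training diary (Intervention) | Yes, per session | Not described |
| Physiotherapist-supervised session, at least weekly (Intervention) | Yes, but only as diary entries | No sessions |
| Phone calls, e-mails, visits (Intervention) | Yes; stated purpose is adherence and progression | Not described |
| 6-week interim assessment (Intervention) | Invited; no event item listed | Not invited |
| PRE and POST (Study design; Assessments and outcome measures) | Attended; no event item listed | Attended; no event item listed |
| Usual-care questionnaire (Participant characteristics) | PRE only | PRE only |
| Clinical examination (Participant characteristics) | Describes the child and selects the most affected leg | Same |
| Analysis (Statistics) | No event summary | No event summary |

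Only the first row is an adverse-event route, and it exists in one arm. Delayed training does not fill the gap. Controls who take it up would presumably keep the diary, but that covers training time and not usual care. The diary logs every training session, supervised or at home, so the missing comparator is not confined to home sessions.

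**How many children a table would rest on.** The Sample size section gives d = 0.8, α = 0.01 and 80% power, and arrives at 39 independent observations per group. An exact two-sided t-test calculation gives 38.19, rounded up to 39, so the figure reproduces. The design effect is 1 + 0.1 × (2 − 1) = 1.1. Then 39 × 1.1 = 42.9, or 43 legs, and 42.9 / 2 = 21.45, or 22 bilaterally affected children. For a mixed group the section gives a size between 39 and 43. The number of children therefore depends on the mix, and I take 22 to 43 per group as an assumed range.

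**What one arm alone can say.** With zero events among n trained children, the one-sided 95% upper bound on the risk is 1 − 0.05^(1/n):
- n = 22: 12.7%
- n = 39: 7.4%
- n = 43: 6.7%

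Even a clean diary would leave these rates open, with no control rate beside them.

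**What two arms could say.** The documents give no event rate, so p is an assumption. If p is the same in both arms, the approximate 95% half-width for the risk difference is 1.96 × √(2p(1 − p)/n):

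| Assumed p | n = 22 | n = 39 | n = 43 |
|---|---|---|---|
| 5% | 13 points | 10 points | 9 points |
| 10% | 18 points | 13 points | 13 points |
| 20% | 24 points | 18 points | 17 points |

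For example, 1.96 × √(2 × 0.20 × 0.80 / 22) = 0.236. The approximation is rough at 5%, where about one event per arm is expected at n = 22. Collecting events in both arms would make a comparison possible, but not a precise one.

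**The case against.** The strongest reply is that the trial does not ask a safety question. Its aim and outcomes are strength, muscle morphology, functional strength, gross motor function and walking capacity, and the mixed models address those. No between-group statement about harm is planned, so under-collection biases no planned estimate. This stands, and it keeps the point minor.

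A second reply is that the diary item sits beside sets, repetitions and fatigue, and so reads as session tolerability monitoring. Session events have no control counterpart under any design. That is fair as a reading of the diary. It also means that nothing in the plan records non-session events in either arm.

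A third reply is that weekly supervised sessions, calls and visits would bring problems to light in children who skip training. They may. The stated purpose of the calls, e-mails and visits is adherence and progression, and none of these contacts is described as asking about events, so the gap remains. Still, a reader who infers that non-adherent children are certainly under-counted goes further than the text: events outside logged sessions may be missed, and no more can be said.

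A fourth reply concerns the remedy. One question at POST relies on 12-week recall by families who know their allocation, put by assessors who also know it. Recall could differ by arm, and the table above shows how imprecise the comparison would be. Both limits stand and must accompany any such table.

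**Conclusion.** The point holds as a minor design gap. The only stated adverse-event collection is per training session. During the randomized 12 weeks the plan therefore describes no event recording for usual-care controls, and events in trained children outside logged sessions may be missed. No between-group risk difference can be estimated from data collected this way.

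This rests on reading silence as absence. The document does not say that events in controls will be ignored, and procedures outside it may exist.

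Stronger readings are not supported:
- A reader might infer that controls will show zero events, so that any diary count looks like harm. Control data would be missing, not zero, and nothing says that zero would be reported.
- A reader might infer that the efficacy results are compromised. No planned efficacy estimate uses adverse-event data.
- A reader might attach an expected number of events to the gap. The documents give no event rate, and any count would also need an assumption about how fully the diary captures events.

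**What to change.** At the existing POST assessment, ask both groups the same short adverse-event questions, with a brief definition and items for severity and relatedness. Ask every trained child, whether or not sessions were logged. Fix the recall window as the 12-week control or intervention period, not the time since PRE, because trained children may start up to 2 weeks after PRE.

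Add one descriptive table to the Statistics section: events and children with events by randomized group. Show session events from the diary separately, because they have no counterpart in controls. State that the table rests on unblinded 12-week recall and supports no powered safety comparison.

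If the questions are repeated after delayed training, present any within-child comparison in waitlist children as descriptive only, because training is confounded with period.

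The cost is a few questions at a visit that already takes place, some data entry and one table. The protocol is dated November 2021, refers to a 2018 design, and describes some conduct in the past tense, so some children may already be past POST. Their control periods cannot be recovered prospectively. For them, state that events were collected during training only and draw no comparative safety conclusion.
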